### 10.2 COMPLIANCE WITH PROTOCOL

All eligible subjects to be treated by [name], [name], [name], and [name] will be counseled on the techniques available for surgical release of the A1 pulley. Enrolled patients in both treatment

arms will be asked to complete POSAS questionnaires as indicated within the schedule outlined in section 6.

The Investigator is responsible for the overall conduct of the study and compliance with the protocol including subject recruitment, IC, screening evaluations, eligibility, assessment/procedure, study evaluations, and any study-related medical care. The Investigator may choose to delegate some of these tasks to suitably trained research staff personnel, but the Investigator is ultimately responsible for these activities.

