## 4 STUDY DESIGN

### 4.1 OVERALL DESIGN

Consecutive patients (until 12 patients are enrolled in each treatment arm) presenting with trigger finger interested in surgical release of the A1 pulley will be offered participation in the study. Additional subjects may be enrolled, as needed to achieve 12 patients in each treatment arm, in the event of patient death or withdrawal from the study. Once enrolled, they will be treated with one of two techniques: endoscopic versus open surgical release. Study measures will include scar assessment based on the Patient and Observer Scar Assessment Scale (POSAS) administered at 1 week, 1 month, and 6 months post-operatively, overall satisfaction (scale of 1 to 10), days before return to work, duration of post-operative occupational therapy, pain medication use, operative time, and complication and recurrence rates.

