#### 4.4 STUDY QUESTIONNAIRES/ASSESSMENT

The patients of [name], [name], [name], and [name] eligible to participate in the study will proceed with baseline assessments once study consents have been signed and the patient has been enrolled in the study.

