### 5.3 INCLUSION CRITERIA

- Male or Female >18 years of age
- Trigger finger, recommended for surgical release
- Be in good health other than the trigger finger
- Have realistic expectations of surgical results
- Be willing to undergo treatment based on the treatment arm to which they are randomized
- Understand and be willing to follow all aspects of the study protocol and have signed and dated the IRB-approved Informed Consent Form and the Authorization for Use and Release of Health and Research Study Information (HIPAA) form prior to any study-related procedures being performed

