### 6.2 STANDARD AND RESEARCH PROCEDURES

All evaluations, procedures performed, and information obtained during pre-operative and post-operative visits will be within the standard of care with the exception of the POSAS questionnaire. The POSAS questionnaire contains a Patient Scale to be completed by the patient and an Observer Scale to be completed by the patient's surgeon-of-record. The Patient Scale is comprised of 6 questions regarding pain, itching, color, stiffness, thickness, and irregularity of their scar scored

numerically from 1 to 10. There is a 7th question, also on a scale of 1 to 10, that asks the patient for their overall opinion of the scar.

The POSAS questionnaire will be completed by patients at 1 week, 1 month, and 6 months post-operatively. In an effort to minimize inconvenience and avoid undue stress to the subjects, they will be given unlimited time to complete the questionnaire and will be allowed to skip questions as desired.

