### 6.3 SURGICAL PROCEDURES

For subjects in open surgical treatment arm: A transverse incision is made at the distal palmar crease overlying the affected digit. Blunt dissection proceeds down to the level of the A1 pulley and the pulley is incised under direct visualization. The surgical site will then be irrigated and closed in usual fashion.

For subjects endoscopic treatment arm: The proximal interphalangeal crease is identified of the affected finger and incised transversely. Blunt dissection is then performed down to the level of the pulley. With the finger held in extension, the EndoSleeve is inserted from distal to proximal at a 15 degree angle. The A1 pulley is visualized via the endoscope. The tip of the EndoSleeve is then situated on the distal edge of the A1 pulley. As the tip is advanced proximally, the blade is seen incising the A1 pulley. The instrument is advanced to a point just before the distal palmar crease. The surrounding tissue is then inspected and the instrument removed. The surgical site is then irrigated and closed in usual fashion.

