## 9.5 EXPLORATORY ANALYSES

POSAS scores at 1 week, 1 month, and 6 months post-operatively will be analyzed between patients treated with endoscopic versus open release using 2-sample t-tests. Differences in pain medication use, days before return to work, duration of OT, operative time, overall satisfaction, complication and recurrence rates between patients treated with endoscopic versus open surgical release of the A1 pulley will be tested for significance using 2-sample t-tests. Additional analyses of possible relationships between outcomes may also be performed using appropriate inferential tests.

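### Four physicians treat the patients, but no rule balances technique within surgeon and no specified comparison accounts for surgeon.

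*Combined protocol and SAP*

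**What the plan says.** - **Who treats.** Section 4.4 draws participants from four physicians: "The patients of [name], [name], [name], and [name] eligible to participate in the study". Section 10.2 names four again as treating: "All eligible subjects to be treated by [name], [name], [name], and [name] will be counseled on the techniques available for surgical release".
- **Who rates.** POSAS has a Patient Scale, completed by the patient, and "an Observer Scale to be completed by the patient's surgeon-of-record" (6.2).
- **Closure.** The open procedure ends with "The surgical site will then be irrigated and closed in usual fashion" and the endoscopic one with "The surgical site is then irrigated and closed in usual fashion" (6.3). No common closure method is described.
- **Assignment.** Section 4.1 says only: "Once enrolled, they will be treated with one of two techniques: endoscopic versus open surgical release". Randomisation appears once, as an inclusion criterion in 5.3: "Be willing to undergo treatment based on the treatment arm to which they are randomized". The synopsis criteria omit it. No sequence, strata or per-surgeon number is given. Sections 4.1, 5.1 and 9.6 fix 12 per arm in total.
- **Analysis.** Section 9.5: "POSAS scores at 1 week, 1 month, and 6 months post-operatively will be analyzed between patients treated with endoscopic versus open release using 2-sample t-tests". The secondary outcomes and operative time are also to be compared by two-sample t-tests. The descriptive summaries in 9.3.1 and 9.3.2 have no breakdown by surgeon, and the subgroup section (9.4) names no factors.

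**The concern.** Surgeon can reach the primary outcome by two routes: how the operation and closure are done, and how severely the Observer items are scored. The second route is not small. Section 9.6 gives a total POSAS range of 12 to 120, and section 6.2 describes six patient items scored 1 to 10, which cover 6 to 60. The remaining 6 to 60 is the Observer part, so half of the possible score comes from a rater who changes with the surgeon.

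The plan does not control for this in either the design or the analysis. A trial in which two surgeons did only endoscopic releases and two did only open releases would meet every written rule. The difference in mean POSAS would then mix technique with operator and rater. This does not depend on anyone favouring a technique: four impartial surgeons who differ in severity would produce it. It would shift the descriptive arm means as well as the p-values.

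**Working it through.** **The plan's own figure.** Section 9.6 takes a difference of 10, SD 8, two-sided 5%, 80% power and equal arms. The exact two-sample t calculation gives 11.09, rounded up to 12 per arm. Power at 12 per arm is 83.3%. The plan's figure reproduces.

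**Inputs.** From the documents: four physicians, 12 per arm, SD 8 (variance 64), unadjusted t-test. Assumed, because the documents give no value: six patients per surgeon, and surgeon explaining 10% or 25% of the variance. The surgeon variance is then 6.4 or 16 (SD 2.5 or 4.0), and the within-surgeon variance 57.6 or 48.

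**Variance of the arm difference.** For surgeon j let w_j = (endoscopic patients − open patients)/12. Then

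Var(difference) = surgeon variance × Σw_j² + within-surgeon variance × (1/12 + 1/12).

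| Endoscopic patients, surgeons 1 to 4 | Σw_j² |
|---|---|
| 3-3-3-3 | 0 |
| 4-4-2-2 | 4 × (2/12)² = 0.11 |
| 5-4-2-1 | 2 × (4/12)² + 2 × (2/12)² = 0.28 |
| 6-6-0-0 | 4 × (6/12)² = 1 |

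- Share 10%: one technique per surgeon gives 6.4 + 57.6/6 = 16.0, SD 4.0. A 3:3 split gives 57.6/6 = 9.6, SD 3.1.
- Share 25%: one technique per surgeon gives 16 + 48/6 = 24, SD 4.9. A 3:3 split gives 48/6 = 8, SD 2.8.

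**Rejection rate of the pooled t-test with no true effect** (100,000 simulated trials per case, nominal 5%):

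| Allocation | Share 10% | Share 25% |
|---|---|---|
| 3-3-3-3 | about 4% | about 3% |
| 4-4-2-2 | about 5% | about 5% |
| 5-4-2-1 | about 6% | about 7% |
| 6-6-0-0 | about 11% | about 21% |
| Random 12:12, surgeon ignored | about 5% | about 5% |

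The 4:2 case stays near 5% because ignoring surgeon also inflates the error variance, which offsets the mild imbalance. At a 5% share, one technique per surgeon gives about 8%.

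**In points.** Suppose two surgeons' patients score 5 points higher than the other two's (assumed). The technique difference is then off by 2 × 5 × 2/12 = 1.7 at 4:2, by 2 × 5 × 4/12 = 3.3 at 5:1, and by 2 × 5 × 6/12 = 5.0 with one technique per surgeon. The target difference is 10.

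**Power for a 10-point difference at 12 per arm.** With 3:3 per surgeon and a model of arm plus surgeon (19 error degrees of freedom), the noncentrality is 10 / (within-surgeon SD × √(1/6)). That is 3.06, 3.23 or 3.54 at within-surgeon SD 8.0, 7.6 or 6.9.

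| Surgeon share | Balanced and adjusted | Unstratified allocation, pooled t-test |
|---|---|---|
| 0 | 82.7% | 83.1% |
| 10% | 86.3% | 84.0% |
| 25% | 91.9% | 85.3% |

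These are simulated values and agree with the noncentral t to within about 0.2 points.

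**Adjustment without balance.** The information left after adjustment, relative to 3:3, is Σ[n₁n₂/(n₁+n₂)]/6:

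- 4:2 and 2:4: (4 × 8/6)/6 = 0.89, power 78.2% at residual SD 8.
- 5:1 and 1:5: (4 × 5/6)/6 = 0.56, power 58.2%.
- 6:0 and 0:6: zero, so the effect cannot be estimated.

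With unstratified random 12:12 allocation and a surgeon term, power at share 0 is 76.9%.

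**The case against.** The strongest reply is that section 5.3 refers to a randomised arm. Under random 12:12 allocation that ignores surgeon, the pooled test holds its 5% level. A reader might note that at least one surgeon would then have a 5:1 or worse split in 43% of trials and infer that the test fails. It does not: within that 43% the rejection rate stays below 7% at both assumed shares, and over all allocations it is about 5%. One technique per surgeon would arise by chance about twice in a million allocations. So the large error rates need assignment that follows the surgeon, and they are a consequence of the missing allocation procedure. This stands, and it limits the point.

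It is also fair that the documents do not report any imbalance, do not say that closure differs between surgeons, and give no estimate of the surgeon share. The t-tests are headed exploratory, and the synopsis justifies 24 patients for descriptive and exploratory work. That softens the weight of a type I error but does not remove the problem: section 9.3 states a directional hypothesis, section 9.6 says the trial is powered for it, and confounding would distort descriptive means too.

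**Conclusion.** The point holds as a gap in the plan: nothing balances technique within surgeon, and no specified comparison accounts for surgeon. Its size depends on how patients are assigned, which the documents leave open. If assignment follows the surgeon completely, the nominal 5% test rejects about 11% or 21% of the time at assumed surgeon shares of 10% or 25%. Mild imbalance is harmless, and true randomisation leaves only a loss of precision.

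Three stronger readings are not supported. A reader might infer that technique is in fact unbalanced across surgeons, but the documents are silent and the actual split is unknown. A reader might infer that no analysis could recover the technique effect; that is true only if every surgeon uses a single technique, and otherwise an arm-plus-surgeon model separates the two at a cost in power. A reader might infer from the closure wording that one method should be imposed in both arms; the text does not show that closure varies by surgeon, and such a rule would set operative practice.

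This is an inexpensive improvement that should be made before enrolment, because balance cannot be added afterwards.

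**What to change.** - **Sections 4.1 and 5.1:** state that assignment is randomised and balanced within surgeon, with surgeon as the stratum and concealed blocks of varying size, among surgeons who perform both techniques.
- **Sections 9.3.1 and 9.5:** present the technique-by-surgeon table, and compare POSAS between arms with surgeon as a stratum (model: arm plus surgeon). Adopt this together with the balance rule, since adjustment alone can lose power.
- **Closure:** at most, record the method used for each patient.

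**Cost.** No extra patients. The model spends 3 degrees of freedom, which lowers power by less than half a point if surgeon explains nothing (82.7% against 83.1%). Small strata make some assignments predictable; varying the block size limits this. Incomplete blocks may leave the arms slightly off 12:12. The documents do not say whether all four physicians perform both techniques; if some do not, recruitment could be slower. Surgeon should be listed as a study variable, since sections 8.3 and 9.2.3 mention the operative record only for operative time.

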### 10.3 STUDY TERMINATION

If conditions arise during the study that indicate that the study should be terminated, the Investigator, Monitor, IRB, and/or regulatory agencies will discuss the situation and take appropriate action after consultation. Conditions that may warrant termination of the study or site include, but are not limited to:

- Discovery of an unexpected, serious, or unacceptable risk to subjects enrolled in the study
- Failure of the Investigator to comply with pertinent national or state regulations, IRB imposed conditions, or protocol requirements
- Submission of knowingly false information from the Investigator to IRB, or any regulatory agency

### 11 ADVERSE EVENTS

Throughout the course of the study, AEs will be monitored and reported on an AE CRF, including seriousness, severity, relationship to device, and action taken. If AEs occur, the first concern will be the safety of the study participants. The Investigator and the research staff will monitor each subject closely, and record any complications that may arise, though not anticipated. Study clinicians will use his/her medical judgment to do whatever is necessary to help treat the problem. Potential risks and/or side effects include:

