## 8.2 SAFETY MEASURES

The incidence and severity of AEs related to the study will be captured. Investigators will inquire about the occurrence of any AEs at all study visits and unscheduled visits. Subjects will also be asked to self-report AEs throughout the duration of the study. Adverse events will be recorded.

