#### 9.2.2 SECONDARY OUTCOME MEASURES

Secondary outcome measures include pain medication use, overall patient satisfaction (score 1 to 10), days to return to work, and duration of post-operative occupational therapy as well as complication and recurrence rates after endoscopic versus open surgical treatment. Complications will include injury to tendons, nerves, and digital vessels noted during or after surgical treatment, as well as surgical site dehiscence and surgical site infections requiring antibiotics. Recurrence will be defined as triggering, confirmed on physical exam by treating physician, at any time point post-operatively.

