#### 9.3.4 SAFETY ANALYSIS

Safety analyses will include the incidence and severity of adverse events observed over the study assessment period. These will be tabulated and presented overall and by relatedness, severity, and preferred term.

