#### 11.1.1 ADVERSE EVENT

An adverse event (AE) is any untoward medical occurrence in a subject that does not necessarily have a causal relationship with the treatment. An adverse event can therefore be any unfavorable and unintended sign (including an abnormal laboratory finding), symptom, or temporal disease, whether or not related to the study assessment(s)/questionnaire(s).

Pre-existing disease or symptoms thereof prior to study enrollment are not considered AEs unless the condition recurs after the subject has recovered from the pre-existing condition, or the condition worsens in intensity or frequency during the study. Normal post-operative sequelae will not be recorded as adverse events. Specifically, normal post-operative pain, swelling, tenderness, loss of skin sensation and ecchymosis within the first two weeks postoperative, requiring normal levels of medication will not be recorded; all abnormal intensity or duration will be recorded and considered an adverse event as well as following the two-week post-operative period.

Adverse events will be monitored throughout the study. At each post-baseline visit, the Investigator will begin querying for adverse events by asking each subject a general, nondirected question such as "Have you had any changes to your condition since your last visit?" Previous adverse events and changes in therapy/concomitant medications should be updated. Directed questioning and examination will then be done as appropriate. All reported adverse events will be documented.

---

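### The only causality rating named for adverse events is relationship to the device, which the open arm does not have, so the planned relatedness breakdown is not comparable between the two operations for events outside the complication list

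*Combined protocol and SAP*

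**What the plan says.** Section 11 sends AEs to a CRF, "including seriousness, severity, relationship to device, and action taken". No other causality item is named there.

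Section 6.3 describes the two operations. In the endoscopic arm "the EndoSleeve is inserted from distal to proximal at a 15 degree angle". In the open arm, "Blunt dissection proceeds down to the level of the A1 pulley and the pulley is incised under direct visualization", and no study device is mentioned. Section 12.3.3, on record retention, also speaks of a single device.

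Section 9.3.4 plans the safety summary as incidence and severity of AEs: "These will be tabulated and presented overall and by relatedness, severity, and preferred term". Treatment arm is not among the listed breakdowns, and the referent of relatedness is not given.

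Other sections use other referents. Section 8.2 says "The incidence and severity of AEs related to the study will be captured". The AE definition in 11.1.1 says that an AE need not be causally linked to the treatment, and then that it counts whether or not it is related to the study's assessments or questionnaires. The same section says "All reported adverse events will be documented".

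Separately, section 9.2.2 makes "complication and recurrence rates after endoscopic versus open surgical treatment" secondary outcomes, and section 9.5 plans a between-arm test of them.

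**The concern.** The trial compares two operations. A causality rating is useful in such a comparison only if it asks the same question in both arms. A rating against the device can be answered yes in one arm only. An AE that the surgeon attributes to the palmar incision has nowhere to be recorded as caused by the study treatment.

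At stake is how harms outside the named complications will be read. Section 2.2 justifies the endoscopic technique partly on the ground that palmar incisions are painful. Prolonged pain or tenderness after open release is thus the kind of harm the study should be able to attribute to the operation, and the one causality item named does not let it. A breakdown by device relatedness would tend to count against endoscopic release, because only that arm can contribute related events.

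**Working it through.** The plan gives no figure on this point, so the check is mainly a reading of the sections side by side.

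**Step 1: can the rating apply in each arm?**

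| | Endoscopic arm | Open arm |
|---|---|---|
| Study device (6.3) | EndoSleeve | none named |
| Related to device possible (11) | yes | no |
| Related to procedure recorded (11) | not named | not named |

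The asymmetry comes from the item itself and does not depend on how investigators use it.

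**Step 2: which harms depend on the AE table?** Three lists have to be compared.

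- Complications and recurrence (8.1.2, 9.2.2): tendon, nerve and digital vessel injury; dehiscence; surgical site infection requiring antibiotics; triggering confirmed on examination. These are compared by arm under 9.5 and need no causality rating.
- Foreseeable risks (section 11): discomfort, pain, redness, swelling, scarring, infection, dehiscence, necrosis.
- Post-operative effects that become AEs when abnormal in intensity or duration, or when present after two weeks (11.1.1): pain, swelling, tenderness, loss of skin sensation, ecchymosis.

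Take from the last two lists what the first already covers, and take out scarring, which is the primary outcome. What remains is prolonged or abnormal pain, discomfort, tenderness, redness, swelling, ecchymosis, necrosis, infection not requiring antibiotics, and sensory loss not classed as nerve injury. Scar pain is also scored within the POSAS, and pain medication use is a secondary outcome, so pain is partly seen by arm elsewhere. As harms, however, these events are summarised only in the 9.3.4 table. Section 9.5 names the outcomes to be tested between arms, including operative time, but not AEs.

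**Step 3: what would the table show?** The counts here are assumptions. Let 3 patients in each arm of 12 have one procedure-caused AE, and let *k* of the 3 endoscopic events be rated device-related.

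- True procedure-caused rate: 3/12 = 25% in each arm.
- Device-related, open: 0/12 = 0%, whatever happens.
- Device-related, endoscopic: *k*/12, which is 0/12 = 0% for *k* = 0, 1/12 = 8.3%, 2/12 = 16.7%, and 3/12 = 25% for *k* = 3.

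The range is needed because, under 6.3, skin incision and dissection come before the EndoSleeve is inserted and closure follows its removal. An endoscopic wound event could reasonably be rated unrelated to the device. At no value of *k* does the rating recover the equal 25% rates.

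On the arm split: 3 events against 0, shown only pooled, would read 3/24 = 12.5% when the arms are 3/12 = 25% and 0/12 = 0%.

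**The case against.** The strongest reply is that the main surgical harms are handled elsewhere. The plan's expectation of no difference (9.3) concerns complications and recurrence, which are compared by arm without any relatedness rating. This stands, and it confines the point to the remaining AEs.

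Some stronger readings are tempting, and the documents do not support them.

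- A reader might infer that the safety data cannot compare the operations. All reported AEs are documented and each patient's arm is known, so a table by arm can be made. Sections 9.3.1 and 9.3.2 also leave out the arm in a plainly comparative trial. The missing arm split alone is an omission in table layout.
- A reader might infer that 8.2 restricts capture to related AEs. The word only is not there. The same section has investigators ask about any AE at every visit and says that AEs will be recorded. It is loosely worded beside 11.1.1, no more.
- A reader might infer that the related rows of the table will certainly hold endoscopic events alone. Section 9.3.4 does not name a referent, the list in section 11 opens with the word including, and the CRF itself is not in the documents. The AE definition also mentions the treatment, which exists in both arms.

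That last reply softens the point but does not remove it. The treatment appears in a definition of what counts as an AE, and no section asks the investigator to rate relationship to it. The one rating that the plan names is against the device.

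**Conclusion.** The point holds in a limited form. As written, the named causality item is asymmetric between the arms, and the relatedness breakdown in 9.3.4 rests on an undefined referent with no stated split by arm. For AEs outside the complication list, that breakdown would not give a like-for-like comparison of the two operations.

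No primary or secondary outcome is affected. The size cannot be derived from the documents, because they give no expected AE rates. Under the assumed equal 25% rates, the apparent gap in related events would lie between 0 and 25 percentage points, depending on how endoscopic events are attributed.

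The conclusion assumes that the CRF carries no causality item beyond the one named in section 11. If it already has a procedure-relatedness field, only the wording and the arm split remain to be settled.

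It is worth correcting before data accrue. The arm split can be added at analysis, but a judgement on relationship to the procedure made long afterwards would not be contemporaneous, as section 12.3.2 requires of source records.

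**What to change.** - **Section 11 and the AE CRF:** record *relationship to the study surgical procedure (endoscopic or open release)* for every AE in both arms. Keep relationship to device as an additional field for the endoscopic arm.
- **Section 9.3.4:** state that AEs are tabulated by treatment arm and, within each arm, by relationship to the procedure, by severity and by preferred term. A pooled column can stay.
- **Section 8.2:** align it with 11.1.1, so that all reported AEs are recorded whatever their cause and relatedness is an attribute rated for each event.

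The cost is one added CRF field, edits to three sections and a slightly longer table. No additional patient data are needed. If AEs have already been recorded under the device-only item, procedure ratings added to them later should be marked as retrospective.
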